**Data Management and Statistical Analysis:**

The patient information will be initially recorded on CRFs which will be stored in the Adult Medicine Unit locking file cabinets, located at the Department of Clinical Medical Sciences, University of the West Indies, St. Augustine. Data will be coded per patient by first letter of first name, first letter of last name followed by numerical date of birth in the order of day, month, and year in a password-protected and encrypted database program in the office of Lecturer [name] at the Department of Clinical Medicine office, [name], Eric Williams Medical Sciences Complex. Each CRF and study database will be reviewed by 2 CRAs to minimize error, and clean and reconcile any conflicting data. We will aim for  $n$  of least 16 patient profiles, see sample size calculations. Any missing information will be censored and thus, not imputed. The study biostatistician will perform routine statistical analyses with SPSS v. 11.0 software (SPSS, Chicago, IL). Continuous variables are expressed as means  $\pm$  SD. Categorical variables are to be expressed as frequencies and percentages. Student's t-test will be used to compare continuous variables. Comparisons between categorical variables will be performed using the two-tailed Fisher's exact test or the Pearson's  $\chi^2$  test, as appropriate. A p-value of  $< 0.05$  will be considered statistically significant. No adjustments for multiple comparisons will be made. Results will be reported as least-square mean  $\pm$  SEM for the detailed analyses.

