***Null Hypothesis:***

There is no difference in response in patients with stable coronary artery disease on DAPT concerning PRUs on dapagliflozin.

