#### *Patient Interview and Case Report Form*

If a patient satisfies the selection criteria from the initial screening process, a physician or CRA-directed interview will then be administered. Demographic and anthropometric data will be recorded on a case report form (CRF). This will comprise the patient's medical and procedural history including any active medications.

Each patient will then be allocated via a computerized randomization program. Patients on DAPT for at least 6 months will be tested for platelet function testing with the P2Y12 VerifyNow assay at baseline. The patients will then undergo at least a 2-week course of dapagliflozin 10mg, followed thereafter by platelet function testing. The study will be randomized via a computer randomization program with a permuted block design and concealment allocation. It is also a controlled, prospective trial design, as group A serves to act as a baseline comparator group and group B has the desired antiplatelet strategy to be investigated over the longitudinal 2-week period. The study will also be blinded as patients will be unaware of their treatment assignments as well as the CRA or physician (Interventional Cardiologist) that performs the platelet function testing.

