### *Aggregation Testing, Platelet Function Testing*

Citrated blood samples are processed by CRAs and study investigators. The platelet function assay to be utilized is the VerifyNow P2Y12 (VN-P2Y12) assay (Accriva, San Diego, California). In brief, the VN-P2Y12 assay is a rapid whole blood point-of-care device that reports results as P2Y12 reaction units (PRU) and percent inhibition of platelet aggregation (%IPA). Assays will be performed as per the instructions of the manufacturer previously described. Please see attached:

- <http://www.accriva.com/uploads/assets/clsi-procedures/14983-revf.docx>
- <http://www.accriva.com/uploads/assets/clsi-procedures/14982-revk.doc>

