**Sample Size Calculation:**

Assuming:

1. A 75 mg/d clopidogrel maintenance dose required at least 5 days and a 600 mg loading dose of clopidogrel required up to 8 hours to achieve  $\sim 50\%$  steady state of inhibition of ADP-induced platelet aggregation.
2. An estimated decrease of 10%, thus achieving a steady state inhibition of ADP-induced aggregation of 55% in patients with dapagliflozin.
3. Type 1 error rate 5%
4. Statistical power of 80%

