**Expected Outcomes of the Study:**

The information obtained from the study would be integral in developing antiplatelet strategies for patients with impaired platelet reactivity. It will advance knowledge in the field i.e. useful for baseline information and hypothesis generation for further studies within the scientific community. It will also determine if dapagliflozin is an adjunct for non-response to the current armamentarium of antiplatelet therapies available in Trinidad and Tobago. This information can then reliably inform regulatory bodies e.g. Ministry of Health (MOH) to make additions to the national Chronic Disease Assistance Medication Program (CDAP) to include this as a possible adjunct to facilitate a more potent antiplatelet effect.

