**Budget:**

Item	Quantity	Purpose/Justification	Total/USD
VerifyNow ASA and P2Y12 PRU Test Kits	2	Test Kits for collected blood samples	~21,000 TTD
Maintenance	N/A	Analyzer needs to be maintained as per Company's policy (located in US - shipping, handling & insurance)	~0 TTD

Stationery	25	25 Informed Consent Forms & Case Report Forms (Triplicate)	~0 TTD
Total			~\$2,000 USD

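### The plan aims for at least 16 patients but cites a calculation giving n = 25; with no SD and no total or per-arm label, the 80% power cannot be reproduced at either number

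*Combined protocol and SAP*

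**What the plan says.** All references are to the combined protocol and SAP.

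- **Data Management and Statistical Analysis** sets the recruitment aim at an n "of least 16 patient profiles, see sample size calculations". The test for continuous variables is Student's t-test at p < 0.05. Missing data are not imputed, and no dropout allowance is given.
- **Sample Size Calculation** starts from about 50% inhibition on clopidogrel and assumes "An estimated decrease of 10%, thus achieving a steady state inhibition of ADP-induced aggregation of 55% in patients with dapagliflozin". It adds a 5% type 1 error and "Statistical power of 80"%. The result is n = 25, with a link to an online calculator whose address indicates a parallel design with a quantitative outcome.
- **Patient Interview and Case Report Form** describes a "computer randomization program with a permuted block design and concealment allocation", with a comparator group A and a dapagliflozin group B, but no allocation ratio.
- **Budget** counts 25 sets of consent and case report forms.
- **Null Hypothesis** is on a different scale from the calculation: "There is no difference in response in patients with stable coronary artery disease on DAPT concerning PRUs on dapagliflozin". The assay section says the device reports both PRU and percent inhibition.

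**The concern.** The statistical section attributes 16 to a calculation that returns 25. A team that stops at 16 would satisfy one section and fall short of the other, and the cross-reference lets 80% power be read as belonging to 16.

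The calculation also cannot be checked. A comparison of two means needs a difference and an SD, and only the difference is given. Whether 25 and 16 are totals or per-arm counts is not stated.

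The risk is an over-read null result. The objective is descriptive and the Expected Outcomes section mentions hypothesis generation, which lowers the stakes. The same section also says "This information can then reliably inform regulatory bodies", and the plan has a formal null hypothesis, a 10% effect hypothesis and a significance threshold. A non-significant result quoted with 80% power would carry more weight than the design supports.

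**Working it through.** **Inputs from the plan.** Difference 55 − 50 = 5 percentage points; alpha 0.05; power 0.80; n = 25 in one place and at least 16 in another; two parallel groups; t-test.

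**Not in the plan.** SD, sidedness of the calculation, allocation ratio, total or per-arm label, dropout. I assume a two-sided test and 1:1 allocation (12/13 for 25 in total, 8/8 for 16 in total). SD means the SD of whatever is compared between arms, either the follow-up value or the change.

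**Step 1: reproduce n = 25.** This is not possible, because the per-arm formula n = 2(z₀.₉₇₅ + z₀.₈₀)² × SD² / 5² has no SD to put in. Treating 50% and 55% as proportions does not rescue it: that needs 1,565 per arm.

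**Step 2: solve for the SD that each number would need.** Power comes from the noncentral t distribution with noncentrality d / √(1/n₁ + 1/n₂), where d = 5/SD. Setting power to 80%:

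| Reading | d for 80% power | Largest SD for 5 points |
|---|---|---|
| 25 total (12/13) | 1.171 | 5/1.171 = 4.27 |
| 16 total (8/8) | 1.507 | 5/1.507 = 3.32 |
| 25 per arm | 0.809 | 5/0.809 = 6.18 |
| 16 per arm | 1.024 | 5/1.024 = 4.88 |

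Some SD gives 80% under every reading, so 25 is not shown to be wrong. But 16 and 25 cannot both be the 80% number for one SD and one counting basis.

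**Step 3: power at 16 if 25 is exactly the 80% number.** Hand check: noncentrality scales with √n, so 2.802 × √(16/25) = 2.802 × 0.8 = 2.242. Then 2.242 − 1.960 = 0.282, which corresponds to about 61%. The exact t results are slightly lower:

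- both totals: 58.7%
- both per arm: 60.0%
- both as a single paired group: 58.9%

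This step needs no assumed SD. If the two counts are on different bases, power at 16 is 33% (25 per arm, 16 total) or 89% (25 total, 16 per arm). The latter would mean 32 patients against 25 budgeted forms.

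**Step 4: power over a range of SDs.** The SDs below are assumptions, not figures from the plan.

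| SD (points) | Power, 25 total | Power, 16 total | Total N for 80% |
|---|---|---|---|
| 3 | 98% | 87% | 2 × 7 = 14 |
| 4 | 85% | 64% | 2 × 12 = 24 |
| 5 | 67% | 46% | 2 × 17 = 34 |
| 10 | 22% | 15% | 2 × 64 = 128 |

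**Step 5: could 16 be 25 after dropout?** That would be a loss of 1 − 16/25 = 36%. The plan states no dropout rate and does not describe 16 as an evaluable minimum.

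**The case against.** The best defence is that the plan attaches 80% only to n = 25. The figure of 16 is a floor, 25 satisfies it, and it may be a stale number or an unlabelled evaluable minimum. The SD may have been entered in the linked calculator, and the 25 budgeted forms suggest that 25 is the total. It is true that no arithmetic error in 25 has been shown. But the sentence containing 16 names the calculation as its source, so the plan itself makes the link. Nothing calls 16 a minimum for analysis, and a stationery line is not a design statement. An SD entered elsewhere is still not reported.

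A second objection is that the SD limits depend on the test. One-sided, 25 in total tolerates an SD of about 4.9. A single-group paired test with n = 25 tolerates an SD of the change of about 8.6. Both figures are right, and the plan states neither sidedness nor pairing. However, the paired figure tests change within one group, which is not the randomised comparison of groups A and B.

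Third, the scale problem is milder than it looks. PRU can be inferred as the main measure from the null hypothesis and from the test repeated at week 2. A rise in inhibition from 50% to 55% is a fall in residual aggregation from 50% to 45%, a relative 10%, which fits the second hypothesis. What remains is that no scale is named as primary, and neither the difference nor the SD is given in PRU.

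**Conclusion.** The concern holds and should be fixed before the plan is relied on. The recruitment aim contradicts the calculation it cites, and the 80% power cannot be reproduced at 16 or at 25 because the SD is missing.

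The firmest figure is the loss from 25 to 16: power falls from 80% to about 59 to 60%. It rests on 25 being exactly the 80% number, a common counting basis, a two-sided 5% test and, for the two-arm readings, 1:1 allocation. The absolute power at either number is unknown until an SD is stated. The finding does not show that 25 is the wrong number. The scale mismatch is secondary.

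**What to change.** 1. State one N, as a total and per arm with the allocation ratio. The budget points to 25 in total. Delete the figure of 16 or reconcile it.
2. Name one primary scale, PRU or percent inhibition, at the sponsor's choice. On that scale give the expected difference, the SD and its source, saying whether the SD is of the follow-up value or of the change. State the sidedness of the test.
3. Restate what that N delivers. With 1:1 allocation and a two-sided 5% test, 80% power corresponds to a difference of about 1.17 SD at 25 in total, or 1.51 SD at 16 in total.
4. If 16 is meant as an evaluable minimum, say so, give the expected loss and state the lower power.

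**Cost.** If the sponsor restates the power or the detectable difference, this is wording only and enrolment is unchanged; the price is a less favourable stated figure. If the sponsor keeps 80% power for 5 points under a two-sided unpaired 1:1 comparison, and the SD exceeds about 4.3 points, more than 25 patients in total are needed: 34 at an SD of 5, 128 at an SD of 10.

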**Hypothesis:**

1. Dapagliflozin attenuates platelet reactivity in patients with diabetes mellitus.
2. Dapagliflozin decreases platelet reactivity by 10%.

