**Study Design:**

The study will be of a prospective, randomized, parallel trial design over 2 years. Patients at the Eric Williams Medical Sciences Complex (EWMSC), Mt. Hope, Trinidad and Tobago will be screened for potential eligibility.

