#### *Blood Sampling, Phlebotomy*

Blood samples for platelet function testing will be collected at baseline before the patients are administered dapagliflozin (baseline sample). Blood will be drawn via an antecubital vein using a 21-gauge needle. The initial 5 mL of all blood samples will be discarded as medical waste as per the institution's policy (to avoid spontaneous platelet activation). Several laboratory tests will be performed including:

1. Complete Blood Count
2. Renal Function Profile
3. Hepatic Function Profile
4. VerifyNow P2Y12 PRU test assay - which will also be performed at the 2nd-week time point after patients have completed their assigned treatment schedules.

Overall, there will be 2 separate instances in which blood sampling/phlebotomy will be performed.

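### The main platelet-reactivity comparison is not specified: an unadjusted t-test with no stated contrast or outcome form, and least-square means with no model; pre-specify ANCOVA on week-2 PRU adjusted for baseline

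*Combined protocol and SAP*

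**What the plan says.** Study Design states: "The study will be of a prospective, randomized, parallel trial design over 2 years". Patient Interview and Case Report Form describes two groups: "group A serves to act as a baseline comparator group and group B has the desired antiplatelet strategy". Blood Sampling, Phlebotomy schedules the VerifyNow P2Y12 assay before treatment and again at week 2, so every patient should have a baseline and a follow-up PRU. The null hypothesis is framed in PRU.

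For continuous variables, Data Management and Statistical Analysis names one method: "Student's t-test will be used to compare continuous variables". The same paragraph ends with "Results will be reported as least-square mean" and SEM for unspecified detailed analyses. No section names a primary analysis, a covariate, ANCOVA, a regression or a mixed model.

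**The concern.** At least three different t-tests fit that sentence: between groups on week-2 PRU, between groups on change in PRU, and paired within group B. They have different precision, and the third answers a different question. The plan does not choose, so the choice could be made after the data are seen.

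The paired reading is not excluded. The treatment description reads as a before-after study: "The patients will then undergo at least a 2-week course of dapagliflozin 10mg, followed thereafter by platelet function testing". The second hypothesis is likewise worded as a decrease. In a paired test, any change shared by both groups (regression to the mean, better adherence to clopidogrel, assay drift) would count as a drug effect.

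Least-square means come from a fitted linear model, so some model may have been intended, but the reader cannot tell which. Baseline PRU is collected in any case, and in a trial this small, leaving it out of the analysis may waste precision.

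**Working it through.** **The plan's own figure.** The Sample Size Calculation gives n = 25 with 5% type 1 error, 80% power and a move from about 50% to 55% inhibition, but no SD, so it cannot be reproduced. Solving backwards (two-sided, 1:1, normal approximation, 25 as total): SD = 5 × √(12.5/2) / (1.960 + 0.842) = 4.46 points, a difference of 5/4.46 = 1.12 SD. With the t distribution and groups of 12 and 13, 80% power needs 1.17 SD.

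**Inputs.** From the documents: two groups, 5% error, and a total of 25 (the Budget lists 25 consent forms) or at least 16 (Data Management and Statistical Analysis). Assumed because not given: 1:1 allocation, a two-sided test, equal SD at both visits, the effect in SD units, and r.

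**Formulas** (variance of the estimated difference in SD² units; power from the noncentral t):
- t-test on week-2 PRU: 1/n₁ + 1/n₂, df N − 2
- t-test on change: 2(1 − r)(1/n₁ + 1/n₂), df N − 2
- ANCOVA: (1 − r²)(1/n₁ + 1/n₂)(1 + 1/(N − 4)), df N − 3; the last factor allows for chance baseline imbalance

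**Example, 12/13, r = 0.5.** 1/12 + 1/13 = 0.1603. The week-2 t-test has 95% CI half-width 2.069 × √0.1603 = 0.83 SD. ANCOVA has variance 0.75 × 0.1603 × (1 + 1/21) = 0.1259 and half-width 2.074 × √0.1259 = 0.74 SD.

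| Groups 12/13 | r = 0 | r = 0.3 | r = 0.5 | r = 0.7 |
|---|---|---|---|---|
| Half-width (SD): week-2 t-test | 0.83 | 0.83 | 0.83 | 0.83 |
| Half-width (SD): change t-test | 1.17 | 0.98 | 0.83 | 0.64 |
| Half-width (SD): ANCOVA | 0.85 | 0.81 | 0.74 | 0.61 |
| Power at 0.8 SD: week-2 t-test | 48% | 48% | 48% | 48% |
| Power at 0.8 SD: change t-test | 27% | 37% | 48% | 70% |
| Power at 0.8 SD: ANCOVA | 46% | 50% | 58% | 74% |
| Power at 1.17 SD: week-2 t-test | 80% | 80% | 80% | 80% |
| Power at 1.17 SD: ANCOVA | 78% | 82% | 88% | 97% |

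ANCOVA breaks even with the week-2 t-test at r of about 0.22 (12/13) or 0.30 (8/8). The change score overtakes ANCOVA only above r of about 0.90 (12/13) or 0.82 (8/8), by at most about 1 power point at 0.8 SD. If 25 is per group, the t-test reaches 80% at 0.809 SD, and ANCOVA runs from 79% at r = 0 to 97% at r = 0.7.

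**Paired reading.** With no drug effect and a shift s (in SD) common to both groups, a paired test in group B (n = 13, df 12) has noncentrality s√13 / √(2(1 − r)). For s = 0.3 and r = 0.5 this is 0.3 × 3.606 / 1 = 1.08.

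| Common shift | r = 0.3 | r = 0.5 | r = 0.7 |
|---|---|---|---|
| 0.3 SD | 13% | 17% | 25% |
| 0.5 SD | 29% | 38% | 57% |

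These are rejection rates with no true effect. Simulation with 40,000 runs per cell agrees to within about 1 point. In the same simulation the three between-group tests rejected in 4.7% to 5.3% of trials at 12/13 and 8/8.

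**The case against.** The documents lean towards a between-group test. The design is called parallel and controlled, group A is the comparator, and the sample-size calculator link is for a parallel quantitative comparison. A stated decrease fits a between-group test equally well. On that reading both t-tests are valid and hold 5%, so the matter is one of efficiency. The gain is also unknown: at r = 0.3 and 0.8 SD it is under 2 points at 12/13 (48.2% to 49.9%) and 0.1 point at 8/8 (32.0% to 32.1%), and it turns negative below the break-even r. The common shifts are illustrations, and the least-square means hint that an adjusted model may have been planned. The stated objective is only descriptive.

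Most of this stands, and it limits the severity. It does not remove the gap: no section states the contrast, the outcome form or the model. The descriptive objective sits beside a formal null hypothesis, an 80% power target and the hope of informing the Ministry of Health. If a model was intended, naming it costs nothing.

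One further caution stands. The treatment sentence in Patient Interview and Case Report Form does not restrict dapagliflozin to group B. It must be reconciled with the description of group A as comparator, because any between-group analysis estimates the drug's effect only if the groups differ in receiving it.

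**Conclusion.** The concern holds. The main comparison is under-specified, and baseline PRU, though collected, has no stated role. On the likelier between-group reading the consequence is lost precision and an open choice of analysis, not bias: at 12/13 ANCOVA changes the CI half-width from 0.83 SD to between 0.85 SD (r = 0) and 0.61 SD (r = 0.7). On the less likely paired reading the conclusion itself could be wrong, with false-positive rates of 13% to 57% under the assumed shifts. All these sizes rest on assumed r, effect and shift, and mainly on reading 25 as the total. The direction does not depend on that reading. This should be corrected before data lock.

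**What to change.** In Data Management and Statistical Analysis, state: *The main comparison is week-2 PRU between the randomized groups by ANCOVA, with treatment group as factor and baseline PRU as covariate. The adjusted (least-squares) mean difference, its 95% CI and the two-sided p-value will be reported.* Name this model as the source of the least-square means, and label any within-group before-after change as descriptive.

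If the hypothesized 10% decrease is to be estimated directly, choose one option in advance: fit the same model to log PRU with log baseline PRU, where a 10% decrease is a ratio of 0.90, or divide the adjusted difference by the comparator group's adjusted mean. PRU is used here because the null hypothesis is about PRU. If percent inhibition, the measure in the sample-size section, is chosen instead, the same model applies with its own baseline.

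The cost is a few sentences and one degree of freedom, with no new data or visits. If r is near 0, the loss is about 2 power points at 12/13 and up to about 4 at 8/8.

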**Sample Size Calculation:**

Assuming:

1. A 75 mg/d clopidogrel maintenance dose required at least 5 days and a 600 mg loading dose of clopidogrel required up to 8 hours to achieve  $\sim 50\%$  steady state of inhibition of ADP-induced platelet aggregation.
2. An estimated decrease of 10%, thus achieving a steady state inhibition of ADP-induced aggregation of 55% in patients with dapagliflozin.
3. Type 1 error rate 5%
4. Statistical power of 80%

**$n = 25$**

([http://hedwig.mgh.harvard.edu/sample\\_size/js/js\\_parallel\\_quant.html](http://hedwig.mgh.harvard.edu/sample_size/js/js_parallel_quant.html))

**Quality Assurance:**

The study will be by GCP and the Declaration of Helsinki. In addition, it will only commence after official approval from the Ethics Committee of the University of the West Indies. There will be no Data Safety and Monitoring Board (DSMB). Patient Informed Consent Forms (ICFs) and Case Report Forms (CRFs) will each be quality-controlled by 2 CRAs and recorded in triplicate (1 for patient records, 2 for the study team).

**Expected Outcomes of the Study:**

The information obtained from the study would be integral in developing antiplatelet strategies for patients with impaired platelet reactivity. It will advance knowledge in the field i.e. useful for baseline information and hypothesis generation for further studies within the scientific community. It will also determine if dapagliflozin is an adjunct for non-response to the current armamentarium of antiplatelet therapies available in Trinidad and Tobago. This information can then reliably inform regulatory bodies e.g. Ministry of Health (MOH) to make additions to the national Chronic Disease Assistance Medication Program (CDAP) to include this as a possible adjunct to facilitate a more potent antiplatelet effect.

